During the development phase of this project, we developed a primary care-based intervention called MOVE! Toward Your Goals (MTG) to facilitate weight management within primary care and increase adoption of intensive VA programs such as MOVE!. The MTG intervention uses a new MTG software tool (that we developed) delivered on tablets to facilitate 5As-based weight management counseling with a health coach and healthcare team to promote goal-setting, behavior change, and weight loss in the primary care setting. The Veteran also receives follow up with 10-15 health coaching calls over 1 year.

As part of a pilot study for a larger, multicenter trial, we will randomize 160 subjects to receive either Enhanced Usual Care or the MTG Intervention.

**Primary Aim:** To explore differences in feasibility, acceptability, and intermediate, behavioral, and weight loss outcomes at 3, 6 and 12 months pre- and post-intervention between the MTG intervention and Enhanced Usual Care. We will explore differences within each arm and compare the 2 intervention arms.

**Hypothesis:** Among obese VA PC patients in an urban primary care practice, a brief, interactive computer-assisted intervention will result in significant improvements in intermediate (self-efficacy, intention, and motivation to change lifestyle behaviors), behavioral (diet and physical activity improvements, adherence to MOVE!), and weight loss outcomes at 3, 6 and 12 months.

**Exploratory Aim:** To compare the intervention arm to a third study arm of non-enrolled PC patients matched for age, gender, and BMI ("Usual Care").

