Patient recruitment overview: We will recruit a consecutive sample of up to 160 overweight/obese patients (120 subjects who complete intervention assuming 25% patient dropout) from the VA primary care clinics. Since this is a pilot study, we may opt to stop recruitment earlier if study proves to be feasible and/or funding is obtained for a larger, cluster randomized efficacy study of the intervention. For Pilot Phase 1, we will obtain an electronic list of obese patients with appointments in the next month for participating providers and the RA will review charts for further eligibility. Lists of eligible patients will be sent to their respective primary care providers who will be asked to determine if any of the patients are medically ineligible to participate (e.g. have a condition where the PCP does not want the patient to engage in lifestyle behavior change). Potential participants will then be sent a letter from both the PI and their PCP describing the study and giving them the opportunity to opt out (i.e. request not to be contacted). Eligible participants will then be offered participation in the study via telephone. This recruitment strategy has been used by my mentor, [name], MPH, and was approved by the VA IRB.

For Pilot Phase 2, we will allow for participating PCPs to refer patients to the study. PCPs will be allowed to contact members of our team via phone or email with the contact information of patients they feel are a good fit for the study. As in the previously mentioned strategies, we will send letters to patients before contacting them by phone to explain the intervention, run through eligibility criteria, and review their medical charts. We will ask these PCP referred patients for permission to review their medical chart to determine medical eligibility. These patients will also be informed that they can opt out of receiving information by calling us.

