## • DATA ANALYSIS

Sample Size and Power Analysis: For weight loss outcomes, we will evaluate pre- and post-intervention in each arm separately and compare two arms. We base our sample size on within-person weight change at baseline and 12 months in each arm. Assuming a mean weight change of at least -2.3kg (SD=5.3) in the MTG intervention arm and no weight change in the Enhanced Usual Care arm, based on a PC-based study of clinical support tools for lifestyle change and a systematic review of technology-assisted weight loss interventions in primary care. Having 60 patients in each arm, the power is 82% to detect this pre- and post-intervention difference in each arm (at the two sided 0.05 significant level). We will also explore weight loss differences between two arms. We do not know how much additional weight loss that telephone support will lead to compared with the enhanced usual care arm. However, if we have 60 patients in each arm and assume the same SD in the weight change, we will have 80% power to detect a 2.8 kg difference between two arms. Assuming 25% dropout rate, we will randomize 160 subjects to obtain 120 evaluable subjects. We conducted sample size calculation using PASS 2008 software.

Statistics Analysis Plan: First, all the variables will be summarized using mean with standard deviation and median with interquartile range for continuous variables and frequency table for categorical variables, overall and by randomized arms, respectively. Mann-Whitney tests for continuous variables and Fisher exact tests for categorical variables will be used to check if baseline characteristics are balanced between two arms. Second, Mann-Whitney tests for continuous outcomes and Fisher exact tests for categorical outcomes will be used to compare outcome variables (including

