intermediate outcomes, behavioral outcomes, and weight outcomes) between two arms at 3 months, 6 months, and 12 months, respectively. Wilcoxon rank tests for continuous outcomes and McNemar tests for binary outcomes will be used to compare them between follow-ups and baseline within each arm. Third, repeated measures modeling based on mixed models will be conducted to compare outcome variables between two arms, utilizing all the data at baseline and three follow-ups. Such modeling can adjust for baseline characteristics, take into account the correlation among repeated measures within subjects, and deal with missing data automatically assuming missing at random. Finally, we will conduct sensitivity analysis based on multiple imputation procedure to examine the impacts of missing data under some missing not at random assumptions.

We will conduct several statistical analyses to describe Veterans participating in the study. Descriptive statistics, including numerical summaries, frequency tables and graphical displays, will be used to present baseline participant characteristics. Exploratory tests, such as chi-square tests and t-tests, will be used to investigate if baseline characteristics are balanced between two randomized arms. Analysis of missing data due to dropout or incomplete surveys will be investigated by inferring a relationship between baseline characteristics/risk factors and 0-1 indicator that defines whether or not a measurement is observed. This analysis will help to identify factors that are likely to be associated with dropout. Additionally, we will investigate whether the dropout rates are different between two arms. For instance, participants with higher levels of motivation may be more likely to be retained in the study. To deal with these missing, we will incorporate the multiple imputation procedure with the regression analyses to be discussed in the following, along with some sensitivity analysis.

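### The 82% within-arm power does not follow from the printed inputs, which give about 91% (paired t-test) or 90% (signed-rank, normal changes)

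*Combined protocol and SAP*

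**What the plan says.** The sample size paragraph (Data Analysis, Sample Size and Power Analysis) names its basis: "We base our sample size on within-person weight change at baseline and 12 months in each arm". It assumes a mean change of at least -2.3 kg with SD 5.3 in the MTG arm, and "no weight change in the Enhanced Usual Care arm". It then claims: "Having 60 patients in each arm, the power is 82% to detect this pre- and post-intervention difference in each arm", at a two-sided 0.05 level.

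The same paragraph adds a between-arm statement for 60 per arm, in which the authors "assume the same SD in the weight change, we will have 80% power to detect a 2.8 kg difference between two arms". On attrition it says: "Assuming 25% dropout rate, we will randomize 160 subjects to obtain 120 evaluable subjects". The patient recruitment overview agrees, giving "120 subjects who complete intervention assuming 25% patient dropout".

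For comparisons of follow-up with baseline within each arm, the Statistics Analysis Plan specifies "Wilcoxon rank tests for continuous outcomes". The Primary Aim is exploratory: "To explore differences in feasibility, acceptability, and intermediate, behavioral, and weight loss outcomes".

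**The concern.** Every input for a one-sample power calculation on paired changes is printed, so a reader should be able to recover 82%. A standardised change of 2.3/5.3 = 0.43 with 60 patients gives clearly more than that. Either the power is misstated, or the mean change, SD, n or test on the page is not the one that was used.

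This is the calculation the plan names as its sample-size basis, and the trial is described as a pilot for a larger multicentre trial. If the misprint is in the assumed change or SD, a wrong planning value could be carried forward.

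The sentence also claims power in each arm, although a -2.3 kg change is assumed in only one of them.

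**Working it through.** **Inputs** (all from the Sample Size and Power Analysis paragraph unless noted)

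- Mean within-person change: 2.3 kg in absolute value, MTG arm.
- SD: 5.3 kg. This is the SD of the change, because the between-arm sentence reuses it as the SD in the weight change.
- n = 60 per arm, already net of dropout: 160 × (1 − 0.25) = 120 = 2 × 60. The recruitment overview agrees.
- Alpha = 0.05, two-sided.
- Planned within-arm test: Wilcoxon on paired data, hence signed-rank (Statistics Analysis Plan).

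**Step 1. Attempt to reproduce 82% with the paired t-test.** Power = P(|T| > t₀.₉₇₅,₅₉), where T is noncentral t with 59 df and noncentrality δ/SD × √n.

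- Noncentrality = (2.3/5.3) × √60 = 0.434 × 7.746 = 3.36.
- Critical value = 2.001.
- Power = **91.1%**. The normal approximation, Φ(3.36 − 1.96), gives 92.0%.

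The stated 82% is not reproduced. Rounding does not explain it: at the least favourable rounding limits (2.25 kg, SD 5.35) the power is still 89.3%.

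**Step 2. The planned signed-rank test.** With normal changes its efficiency relative to the t-test is 3/π, so the effective n is 60 × 0.955 = 57.3 and the power is **89.8%**. Simulation with normal changes agrees, at about 90%.

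Skewness would move this figure. With shifted-gamma changes of the same mean and SD, simulated signed-rank power is about 84% at skewness −0.7, about 82% at −1.0, about 94% at +0.7 and about 95% at +1.0. These shapes are assumptions for illustration, since the plan states no distribution.

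**Step 3. What would give about 82%?**

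| Route | Power | Conflict with the text |
|---|---|---|
| Change of 2.0 kg (n = 60, SD 5.3) | 82.0% | 2.3 kg is printed |
| SD of 6.1 kg (n = 60, 2.3 kg) | 81.9% | 5.3 kg is printed |
| n = 46 | 82.1% | 60 is printed |
| n = 45 (25% taken off 60) | 81.2% | 60 is already net of dropout |
| Alpha 0.05/3 | 81.2% | 0.05 is printed |
| Detection in both arms, t-test: 0.911² | 83.0% | No change is assumed in Enhanced Usual Care |
| Detection in both arms, signed-rank: 0.898² | 80.6% | As above |
| Signed-rank, skewness near −1.0 | about 82% | No distribution is printed |

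A two-sample t-test at 2.3 kg gives 65.5%, so a mix-up of the two designs does not explain the figure either.

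**Step 4. Check the method on the rest of the paragraph.**

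- Between arms, 60 per arm, 2.8 kg, SD 5.3: noncentrality = 2.8/(5.3 × √(2/60)) = 2.89. Power is 81.9% by t-test, or 80.1% by Mann-Whitney with 3/π efficiency. The plan states 80%.
- Dropout: 120/0.75 = 160, as stated.

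Both reproduce. Only the within-arm figure fails.

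**The case against.** The strongest alternative uses only printed numbers. If power in each arm means detecting the change in both independent arms, the joint power is 83.0% (t-test) or 80.6% (signed-rank), on either side of 82%. On that reading the fault would be unclear wording, not wrong arithmetic. But neither value is 82%, and the reading requires a 2.3 kg change under Enhanced Usual Care, where the plan assumes none. Reading the phrase as a change of this size in either arm, taken separately, returns about 91%.

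Three further cautions stand:

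- The error is conservative only if the printed inputs are the right ones. If the true assumption was 2.0 kg or an SD of 6.1 kg, 82% is correct and the input is the misprint. Writing 91% would then overstate the power.
- The skewness results show that a distributional assumption could matter. They are not evidence that one was used.
- The practical consequence is small. This is an exploratory pilot, recruitment may stop early under the plan, and no decision rule depends on this figure.

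**Conclusion.** The concern holds as a minor error. As written, the within-arm power should be about 91% (paired t-test), or about 90% (signed-rank, assuming normal changes), not 82%. Every route found to a figure near 82% either contradicts a printed value or needs an assumption the plan does not state. The documents do not show which, if any, was used.

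The conclusion assumes that 5.3 kg is the SD of the change and that 60 is the evaluable number per arm; the text supports both. Nothing else in the paragraph changes: 60 evaluable per arm, 160 randomised, and 80% between-arm power for 2.8 kg.

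**What to change.** First check the stored output of the sample size software for the test, mean change, SD, n and any distribution that were entered.

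If the printed inputs are confirmed, replace the sentence with:

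> With 60 evaluable patients in the MTG arm, power is about 91% (paired t-test; about 90% with the Wilcoxon signed-rank test if changes are normally distributed) for a mean within-person change of -2.3 kg (SD of change 5.3) at two-sided 0.05. Enhanced Usual Care is assumed to show no change, so no within-arm power is claimed for that arm.

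If the output shows that 82% came from other inputs, print those inputs and keep the power that belongs to them, again naming the arm to which it applies.

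The cost is one rewritten sentence and one check of a stored file. On the printed inputs, neither the number of patients nor the number randomised changes.

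### Between-arm tests at 3, 6 and 12 months ignore baseline, and the planned mixed model names no 12-month arm contrast; specifying it with baseline adjustment is a minor, free improvement

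*Combined protocol and SAP*

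**What the plan says.** The Statistics Analysis Plan paragraph (Data Analysis) sets out two between-arm analyses.

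- **Visit by visit.** "Mann-Whitney tests for continuous outcomes and Fisher exact tests for categorical outcomes will be used to compare outcome variables" between arms, separately at 3, 6 and 12 months. No covariate is mentioned. The sentence does not say whether the variable is the visit value or the change from baseline.
- **Mixed model.** Repeated-measures modelling "will be conducted to compare outcome variables between two arms, utilizing all the data at baseline and three follow-ups". On covariates it says only: "Such modeling can adjust for baseline characteristics". The terms of the model, the arm contrast and its priority relative to the Mann-Whitney tests are not given.

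For weight, other text points to change. The Primary Aim refers to "weight loss outcomes at 3, 6 and 12 months pre- and post-intervention between the MTG intervention and Enhanced Usual Care". The Sample Size and Power Analysis paragraph begins "For weight loss outcomes, we will evaluate pre- and post-intervention in each arm separately and compare two arms" and later adds "We will also explore weight loss differences between two arms". Its between-arm power statement asks the reader to "assume the same SD in the weight change" and concludes that "we will have 80% power to detect a 2.8 kg difference between two arms" with 60 patients per arm.

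For the other continuous outcomes the Measurements section is less clear. Physical activity outcomes are defined as changes. The dietary and most intermediate outcomes are not defined as either value or change.

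**The concern.** This is a pilot for a larger trial. Its most useful between-arm result is an estimated 12-month difference with a confidence interval. A Mann-Whitney p-value does not supply one, and an unadjusted test leaves unused the baseline values that the study already collects.

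The mixed model could supply the estimate, but as written it covers quite different models. One has the follow-up visits as responses, an arm-by-visit term and baseline as a covariate; it gives an efficient 12-month contrast. Another has all four visits as responses and a single arm effect. It mixes in the baseline visit, where randomization makes the expected difference zero, and so pulls the estimate toward zero. With no main analysis named, the choice between these, and between either and the rank tests, could be made after the data are seen.

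**Working it through.** **Inputs from the Sample Size and Power Analysis paragraph:** 60 evaluable per arm, SD of weight change 5.3 kg, between-arm difference 2.8 kg. Two-sided 0.05 is stated for the within-arm test and is assumed here for the between-arm test as well.

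**Assumed, not in the documents:** between-person SD of weight s = 10 to 25 kg, equal at baseline and 12 months; for the other outcomes, a true difference of 0.5 SD and baseline correlation r = 0.3 to 0.7. Data are taken as normal and complete unless stated.

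**1. The plan's own figure.** Power is from the noncentral t with noncentrality d / (SD × √(2/n)). Mann-Whitney under normality uses an effective n of 60 × 3/π = 57.3 per arm.

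- t-test on change: 2.8 / (5.3 × √(2/60)) = 2.89, power 81.9%.
- Mann-Whitney on change: power 80.05%.

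The stated 80% is reproduced by Mann-Whitney on change.

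**2. Baseline-adjusted 12-month contrast for weight.** The change SD fixes the correlation: r = 1 − 5.3² / (2s²). The residual SD is s√(1 − r²). The 95% CI half-width is t(0.975; 117) × residual SD × √(2/60).

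| Assumed s (kg) | r | Residual SD (kg) | Power | CI half-width (kg) |
|---|---|---|---|---|
| 10 | 0.860 | 5.11 | 84.5% | 1.85 |
| 15 | 0.938 | 5.22 | 83.0% | 1.89 |
| 20 | 0.965 | 5.25 | 82.5% | 1.90 |
| 25 | 0.978 | 5.27 | 82.3% | 1.91 |

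Against 80.05%, the gain is about 2 to 4.5 points. Against a t-test on change (81.9%), adjustment itself adds only 0.4 to 2.6 points.

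**3. Sensitivity to normality.** I simulated the same weight setting at s = 15 and 20 kg, replacing normal errors by t errors with 5 df and the same variance. Mann-Whitney on change then has about 87-88% power and the adjusted contrast about 82-83%. With 10 df the two are nearly equal, at about 82-83%. The ranking under normality does not carry over to heavy tails.

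**4. Dilution under an arm main effect.** Suppose all four visits are responses, with visit effects, a single arm effect, compound symmetry, and a full 2.8 kg difference from month 3 onward. The arm estimate is the average difference over visits: (0 + 2.8 + 2.8 + 2.8) / 4 = 2.1 kg, a 25% attenuation. This does not depend on s.

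**5. Other continuous outcomes, 0.5 SD difference, 60 per arm.** In units of the visit variance, the variances are 1 (visit value), 2(1 − r) (change) and 1 − r² (baseline-adjusted).

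| Assumed r | Mann-Whitney, visit value | Mann-Whitney, change | Baseline-adjusted |
|---|---|---|---|
| 0.3 | 76% | 61% | 81% |
| 0.5 | 76% | 76% | 88% |
| 0.7 | 76% | 93% | 97% |

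Adjustment cuts the variance by 9%, 25% and 49% against the visit value, and by 35%, 25% and 15% against change. Part of the power difference in this table comes from moving from a rank test to a t-type test.

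**The case against.** The strongest reply is that the plan already contains most of the remedy. It commits to a mixed model between arms that uses baseline and all follow-ups, allows for within-person correlation, handles missing data under missing at random and can adjust for baseline. That is right: the model needs specifying, not adding.

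A second reply is that a rank test is a reasonable choice for weight change and for survey measures such as servings or beverage intake, which may be far from normal. This also stands. Step 3 shows that the rank test can be the more powerful, so a claim that adjustment is always best would be wrong.

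Third, the missing specification of value or change is less open than the analysis sentence alone suggests. For weight, the aims and the power paragraph speak of loss and change. For the other outcomes, the pre/post wording of the Primary Aim leans the same way, though it does not settle the matter.

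A reader might infer that the plan tests raw visit weights and so loses most of its power. The same calculation on visit weights gives 32%, 17%, 12% and 9% for s = 10, 15, 20 and 25 kg. The documents do not support that inference: their wording indicates change, their 80% is reproduced on change, and they give no between-person SD.

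**Conclusion.** The point holds as a minor, free improvement. The visit-by-visit between-arm tests are unadjusted, and the planned mixed model fixes neither the baseline adjustment nor a 12-month arm contrast.

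For weight, on the change reading that the text supports, power moves from 80% to about 82-85% under normality, and the advantage can reverse with heavy tails. The real gain for weight is an interpretable 12-month estimate with a 95% CI of about ±1.9 kg. For survey outcomes the gain in precision can be larger: 81-97% power against 76% on visit value or 61-93% on change. Those figures rest on an assumed 0.5 SD difference, assumed correlations of 0.3 to 0.7 and normal data.

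The dilution to 2.1 kg describes a model that the text allows, not one that it states. It would be wrong to conclude that the sponsor will fit it. Nor does any of this invalidate the study: the between-arm comparison is exploratory, the sample size rests on within-arm change, and the within-arm tests are unaffected.

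**What to change.** In the Statistics Analysis Plan paragraph:

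- For continuous outcomes with a baseline measurement, specify the planned mixed model as the 3-, 6- and 12-month values on arm, visit, arm-by-visit and the baseline value of the same outcome. Modelling baseline as a response with the arm means constrained equal is an acceptable alternative.
- Name the 12-month arm difference with its 95% CI as the main between-arm estimate.
- Keep the Mann-Whitney tests as supporting analyses robust to non-normal data, and state that for weight they are on change from baseline.
- Leave outcomes without a baseline value, such as goal attainment, as follow-up comparisons.

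The cost is wording only. Weight, waist circumference, diet and physical activity are already measured at baseline, so no patients, visits or procedures are added.

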**C. RESEARCH DESIGN AND METHODS**

**OVERVIEW**

The first 10-12 participants in the MTG intervention will not be randomized to ensure that the intervention can be implemented within PACT. We will then conduct a randomized, controlled pilot study in the VA NYHHS primary care clinic to test the feasibility of implementation and acceptability of the MOVE! Toward your Goals (MTG) intervention for patients and providers. There are two distinct phases of the randomized intervention: Pilot Phase 1 and Pilot Phase 2. We will assess intermediate (e.g. self-efficacy, goal attainment, motivation to lose weight), behavioral (diet and physical activity) outcomes, and weight loss at 3, 6, and 12 months. Pilot Phase 2 is a continuation of Pilot Phase 1, however the methods of recruitment and sequence of events will be modified to maximize ease and enrollment.

In both phases, we will train participating PACT teamlets and health coaches to facilitate goal setting and conduct motivational interviewing to facilitate goal setting and conduct brief telephone counseling so that they can deliver the intervention. We will recruit primary care patients and randomize to either receive the MTG intervention or Enhanced Usual Care. On the first Baseline study visit, all participants will complete a Baseline Survey and obtain weight and height measurements.

Those in the MTG intervention group will then complete the MTG tool on a tablet computer, receive a binder of personalized materials generated by the tool, and receive a 15-20 minute counseling session about weight loss and lifestyle goals with a Health Coach (research team member). Participants randomized to the Enhanced Usual Care control will receive a handout about local MOVE!

programs and selected VA MOVE! and Healthy Living Message handouts related to weight management.

After this Baseline study visit, participants in the MTG intervention group will receive 10-15 follow up counseling phone calls with the health coach to review goals over a 12 month period. In Pilot Phase 1, participants will meet with their PCP during their regularly scheduled visit before taking an exit survey. In Pilot Phase 2, participants will meet with their PCPs at any point during the course of the one year intervention. During the visit, RN care managers and the PCPs will be prompted in CPRS to read a CPRS Research Note entered by a Health Coach. It will summarize the

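### Coaching is given in the MTG arm only, but no planned between-arm analysis allows for patients sharing a coach; the 80% power at 2.8 kg holds only if coach clustering is negligible

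*Combined protocol and SAP*

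**What the plan says.** **Who is coached.** Under Research Design and Methods, Overview, "participants in the MTG intervention group will receive 10-15 follow up counseling phone calls with the health coach" over 12 months, after a coaching session at the baseline visit. Under Study Arms/Randomization, Enhanced Usual Care patients receive handouts in place of the tool and the coaching. The coaches are research assistants trained for the role (PCP and Health Coach Recruitment and Training Overview). Their number, their caseloads and the rule for assigning patients to them are not given.

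**How outcomes are analysed.** The Statistics Analysis Plan compares the arms at each visit with Mann-Whitney and Fisher exact tests. It then fits mixed models to all visits, which can "take into account the correlation among repeated measures within subjects". No coach term appears in any analysis.

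**Power.** The Sample Size and Power Analysis paragraph bases the sample size on within-arm weight change and treats the between-arm difference as something to explore. For that comparison it says "if we have 60 patients in each arm and assume the same SD in the weight change", then "we will have 80% power to detect a 2.8 kg difference between two arms". It gives no design effect, ICC or coach count. The sample size follows from "Assuming 25% dropout rate, we will randomize 160 subjects to obtain 120 evaluable subjects".

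**The concern.** Patients are randomized individually, but in one arm the treatment is delivered by people who each serve several patients. If some coaches get better results than others, patients with the same coach will have correlated outcomes. This can happen in the MTG arm only. Sharing is unavoidable unless there are nearly as many coaches as patients.

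A standard error computed as if MTG patients were independent omits the between-coach part of the variance. Confidence intervals for the difference between arms would then be too narrow, a nominal 5% test would reject too often, and the stated power would be too high. A random effect for subject does not repair this, because it accounts for repeated visits by one patient and not for different patients of one coach.

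**Working it through.** **Inputs from the documents (Sample Size and Power Analysis)**
- 60 evaluable patients per arm; 120/(1 − 0.25) = 160 randomized, so about 80 per arm.
- SD of weight change 5.3 kg: "Assuming a mean weight change of at least -2.3kg (SD=5.3) in the MTG intervention arm", with the same SD taken in the control arm.
- Difference 2.8 kg. Alpha is "at the two sided 0.05 significant level"; the plan states this for the within-arm figure, and I take it to apply between arms too.

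**Inputs not in the documents (assumptions)**
- Number of coaches K: 2 to 10, with equal caseloads of 60/K evaluable patients and one coach per patient.
- Coach ICC: 0.01 to 0.05.
- Total SD held at 5.3 kg.
- Inference to coaching of this kind, not only to these particular coaches.

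**Step 1: reproduce the stated 80%.** With independent patients, SE = 5.3 × √(2/60) = 0.968 kg.
- Normal approximation: Φ(2.8/0.968 − 1.96) = 82.5%.
- Two-sample t-test (noncentral t): 81.9%.
- Mann-Whitney, taking 60 × 3/π = 57.3 effective patients per arm: 80.1%.

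The plan's figure is therefore a two-sample calculation on weight change with fully independent patients. It does not come from the mixed model.

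**Step 2: allow for coach clustering in the MTG arm.**
- Design effect in the MTG arm: D = 1 + (60/K − 1) × ICC.
- Ratio of true to assumed variance of the difference: R = (D + 1)/2, since only one arm is inflated.
- True SE = 0.968 × √R.
- Type I error of the unadjusted test = 2 × [1 − Φ(1.96/√R)].
- Power at 2.8 kg of a test using the true SE = Φ(2.8/true SE − 1.96).
- Difference detectable with 80% power = (1.96 + 0.84) × true SE.

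| K | ICC | D | R | True SE (kg) | Type I error, unadjusted | Power at 2.8 kg | Detectable at 80% (kg) |
|---|---|---|---|---|---|---|---|
| – | 0 | 1.00 | 1.000 | 0.968 | 5.0% | 82.5% | 2.71 |
| 10 | 0.01 | 1.05 | 1.025 | 0.980 | 5.3% | 81.5% | 2.74 |
| 4 | 0.02 | 1.28 | 1.140 | 1.033 | 6.6% | 77.3% | 2.89 |
| 2 | 0.05 | 2.45 | 1.725 | 1.271 | 13.6% | 59.6% | 3.56 |

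For the last row: D = 1 + 29 × 0.05 = 2.45; R = 3.45/2 = 1.725; SE = 0.968 × 1.313 = 1.271; power = Φ(2.203 − 1.96) = 59.6%.

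The type I error and power columns describe different tests: the first is the planned test, which ignores coach, and the second is one with the correct SE.

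**Step 3: small-sample degrees of freedom.** The normal approximation is kind to designs with few coaches. With Satterthwaite degrees of freedom (K − 1 for the MTG mean), power at 2.8 kg is 79% for 10 coaches at ICC 0.01, 68% for 4 at 0.02, and 25% for 2 at 0.05. The first is close to the 81.9% of the ordinary t-test; the last rests on about 2 degrees of freedom.

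All of this is for a two-sample comparison of weight change. The exact inflation for the Mann-Whitney test or the mixed model would differ somewhat.

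**The case against.** The strongest answer is that nothing in the documents shows the standard error to be wrong. No coach count or ICC is given. With 10 coaches and ICC 0.01, power falls by one percentage point and type I error rises by 0.3. A common software tool, tool-generated materials and shared training may keep differences between coaches small. Strict nesting is also not established: the description of the MTG intervention lets another member of the care team make the calls, and no passage says that a patient keeps one coach throughout. If callers vary, the simple design effect does not describe the design exactly. Finally, this is a pilot sized on within-arm change, and no decision rule depends on the between-arm test holding 5%.

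Most of this stands. It makes the point conditional and keeps its weight modest. It does not remove it: shared or varying callers can still induce correlation, and as written the plan offers no way to find out which case applies.

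Two further readings are tempting and should be resisted.
- *A PCP effect is needed as well.* Patients are randomized individually, not by PCP, and participating PCPs see patients in both arms. PCP effects should therefore be largely balanced, and the documents give no reason to think they distort the between-arm SE.
- *The pilot fails to supply the variance component its successor needs.* The Patient recruitment overview mentions a cluster randomized study only as one condition for stopping recruitment early ("funding is obtained for a larger, cluster randomized efficacy study of the intervention") and does not name the cluster. An ICC from a handful of coaches would be very imprecise in any case.

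**Conclusion.** The omission is real: coaching is in one arm only, and neither the tests, the mixed model nor the power sentence allows for it. The consequence is conditional. If the coach ICC is above 0, the between-arm SE is too small and the 80% at 2.8 kg is optimistic; if it is essentially 0, the plan's figure stands.

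Over the assumed range of 2 to 10 coaches and ICC 0.01 to 0.05, power by the normal approximation lies between 81.5% and 59.6% (82.5% without clustering). The type I error of the unadjusted test lies between 5.3% and 13.6%. A reader might infer that coaches are few and the SE is definitely understated; the documents do not support that, because coach count, ICC and assignment are all unstated. Since the comparison is exploratory, what is at stake is the honesty of the interval and of the power statement, not a confirmatory conclusion.

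**What to change.** 1. **Data.** Record the coach ID for the baseline session and for each call, including calls made by another team member.
2. **Design description.** State the number of coaches and the rule by which patients are assigned to them.
3. **SAP.** Keep the planned analyses and add a pre-specified sensitivity analysis of the between-arm weight comparison, with a coach random effect in the MTG arm only and small-sample degrees of freedom. If there are too few coaches to fit this, report the between-arm interval with its SE multiplied by √R for ICC 0.01 to 0.05, using the actual number of coaches. For the two-sample comparison the multiplier is 1.07 to 1.31 with 2 coaches and 1.01 to 1.06 with 10.
4. **Power sentence.** Say that the 80% at 2.8 kg assumes no coach clustering, and give the power for a short range of coach numbers and ICCs.

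The cost is one ID field and a few sentences, with no change to treatment or sample size. The downside is wider intervals in the sensitivity analysis, much wider with 2 or 3 coaches: for 3 coaches at ICC 0.05, the Satterthwaite calculation has about 4.5 degrees of freedom and 47% power at 2.8 kg. The coach variance component will also be imprecise. For these reasons the coach model is proposed as a sensitivity analysis and not as the main one.
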